## 8. Measurements and investigations

Questionnaire: The research staff will apply a questionnaire obtaining information on history about fatty liver and hyperglycemia, comorbidity and concomitant drug use (such as fatty liver, diabetes, hypertension, dyslipidemia and cardiovascular disease), lifestyle risk factors (cigarette smoking, alcohol drinking and physical activity).

Dietary record: The research staff will provide an electronic kitchen scale to subjects enrolled. Subjects are required to record the name and weight of food they eat in a whole day on a distributed form. After the diet record is finished, they should take a photo of form and send to dietitian in research group. The form is as followed. They are required to record food intake for 3 days before day 0 and the average of calorie consumption will be used as baseline reference. During intervention, subjects in both groups will get distributed blank forms in each visit and are required to record their diet every day.

\_

		Date							
		Brea	akfast	Lu	ınch	Di	nner	Extra	meals
lter	n	Food	Weight (g)	Food	Weight (g)	Food	Weight (g)	Food	Weight (g)
	Rice								
Staplo	Noodles								
Staple food	Coarse grain								
	Tubers								
	Pork								
	Beef and mutton								
Meat	Chicken and duck								
	Fish and shrimp								
	Others								
Egg	IS								
	Milk								
Dairy food	Yogurt								
	Others								
Bean	Bean curd								
products	Soybean milk								
Vegetables	1								

Table 3. Dietary form

	2				
	3				
	4				
	1				
Fruits	2				
	3				
Nut	S				
	Beer				
Alcoholic	Grape wine				
drinks	Millet wine				
	Baijiu				
Non-alcoho	lic drinks				
Oils	S				

Activity (steps): During the intervention, subjects need to wear a smart electronic wearable device (Redmi Smart Band, Xiaomi Corporation, China) to record the daily steps automatically.

Physical measurements: At the clinic visit, trained staff will take measurements of body weight, height, waist circumference, blood pressure according to standard procedures. Subjects should avoid wearing shoes and heavy clothes when measuring body weight. Mid-way between the lower border of rib margin and the upper border of iliac crest will be measured as waist circumference. The blood pressure will be measured after resting for 5 minutes in a sitting position and alcohol, cigarettes, coffee/tea and physical exercise will be avoided within 30 minutes before the measurement. Automatic sphygmomanometer will be applied for standardized detection.

Laboratory measurements: Blood samples will be drawn 10 hours after fasting and be used to measure blood glucose, HbA1c, liver enzymes, serum creatinine, urine acid and lipids.. High performance liquid chromatography (HPLC) method will be used for measuring HbA1c. Total cholesterol, high-density lipoprotein cholesterol, triglycerides, free fatty acids, electrolytes, liver enzymes, serum creatinine and urine acid will be measured by a model 7600 automated bioanalyzer (Hitachi, Tokyo, Japan). Low-density lipoprotein cholesterol will be calculated by the Friedewald equation. The FBG and 2-hour postprandial blood glucose in oral glucose tolerance test will be tested following a standard 75g oral glucose tolerance test and measured using the glucose oxidase method. An electrochemiluminescence immunoassay will be used to measure the fasting and 2-hour postprandial insulin. All parameters are tested in the clinical biochemical laboratory of Zhongshan Hospital affiliated to Fudan University. The clinical testing laboratory will adopt the standardized process and obtain the corresponding certification qualification.

H-MRS: Whole liver fat content by H-MRS was performed with a 1.5T MRI Scanner (Siemens Healthineers, Germany). Firstly, T1-weighted sagittal, coronal, and axial images were acquired for the localization of the spectroscopy acquisition voxel. A single 2×2×2 cm voxel was placed within the right lobe avoiding major vascular structures and subcutaneous fat tissue. The proton spectrum was acquired after shimming over the volume of interest by means of a point-resolved spectroscopy sequence with the following parameters: repetition time = 1500 ms and echo time = 135 ms. Signal intensities of the water peak at 4.8 ppm (Sw) and the fat

peak at 1.4 ppm (Sf) were measured, and the hepatic fat percentage was calculated as a ratio of the signal from the methylene group to the total signal of methylene and water.

MRI-PDFF: MRI examinations were performed on a 3.0T MRI scanner (Ingenia CX 3.0 T, Philips Healthcare, USA). The quantitative calculation of fat fraction requires the use of MRI mDIXON-Quant BH or FF sequences, because the dicom header information of these sequences already contains the value of fat fraction. However, the profile of the liver is not clear in these sequences, so we first use the deep learning neural network to predict the outline of the liver and the eight segments of the liver on the in-phase of dixon as it has a clear view of the liver. Then resample these two labels to the mDIXON-Quant BH or FF sequence, and correspond to the location of each slice of these two sequences. In this way, the liver profile label and liver Couinaud segment label on the fat sequence are obtained. Afterwards, the corresponding matrix is obtained by multiplying the mDIXON-Quant BH or FF sequence with the liver profile and liver Couinaud segment label matrix. Finally, the corresponding fat fraction mean and upper-lower percentiles of every liver segment can be calculated according to different needs. It should also be noted that the fat fraction values in different machines or sequences are in different units and need to be divided again by the corresponding ratios to obtain the final results. The neural network used for predicting liver profile and liver Couinaud segment is a 2.5D UNet. The input of this network is a multi-layer 2D matrix, and residual modules and channel attention mechanism modules are added on the basis of UNet. The training dataset Including more than 200 cases with manually corrected liver profile and liver Couinaud labels and from Quanjing Imaging Center and Zhongshan Hospital Affiliated to Fudan University. The ratio of training, verification and test datasets is 4:1:1, and the inference dice of the model test set is respectively 0.981 for liver profile and 0.804 for liver Couinaud segment.

Transient elastography: The controlled attenuation parameter (CAP) in dB/m and Liver stiffness measurement (LSM) in kPa will be measured using FibroScan (FibroScan 502 Touch, Echosens, France). All subjects will be detected when holding breath in supine position by using the M probe. Each subject collected at least 10 valid measurements. Only when the proportion of effective measurement times to the total measurement times is  $\geq$  60%, the interquartile range (IQR) of repeatedly collected CAP value is  $\leq$  40 dB / m, and the IQR of repeatedly collected LSM value is  $\leq$  30%, can the result be considered reliable. The median value will be kept as a representative result.

Body composition: Lean mass and fat mass were measured by a bioimpedance analyzer Inbody520 (Biospace, Seoul, Korea). Specifically, for the area of abdominal adipose tissue, MRI (1.5 T, Siemens Avanto, Erlangen, Germany) were applied to conduct abdominal positioning scanning first, and then H-MRS detection. Sections will be acquired through the abdomen at the level of umbilicus to L4. Subcutaneous adipose tissue (SAT) and visceral adipose tissue (VAT) will be measured with NIH image software (ImageJ 1.41o; National Institutes of Health, Bethesda, MD, USA).

Blood samples in weeks 0 and week 12 were collected for metabolomics analysis. Feces samples in weeks 0 and week 12 were collected for detection of gut microbiome and gut microbiota-derived metabolites. Resting state cerebral functional magnetic resonance imaging was conducted before and after intervention to explore the effects of intervention on brain structure, network connectivity, and other parameters of brain functions.

# 9. Adverse events (AE)

### 9.1 Definition

Non-Serious Adverse Event (NSAE) refers to an unforeseeable medical condition that occurs during or after the treatment, or an event that makes the original condition worse. The occurrence of NSAE does not necessarily have a causal relationship with the intervention. Adverse medical conditions include symptoms (such as nausea and chest pain), physical signs (such as tachycardia and hepatomegaly) or abnormal examination results.

Serious adverse event (SAE) refers to the adverse event that meets one or more of the following criteria caused by intervention in screening method, treatment period, cleaning period or follow-up period:

1) Causing death;

- 2) Life-threatening injury;
- 3) Leading to longer hospitalization;
- 4) Causing continuous or obvious disability;
- 5) Congenital malformation/defect;

6) Major medical events that may cause injury to the subject or require medical intervention to prevent its occurrence.

Severity grading of non-serious adverse events:

1=mild (with symptoms or signs, but tolerable)

2=moderate (feeling unwell and affecting normal activities)

3=severe (inability to perform normal activities)

The unresolved NSAE at the end of the trial need to be followed up. The follow-up interval and duration depend on the medical needs. For the unsolved adverse events at the end of the trial or when the subjects withdraw from the study, the follow-up shall be conducted until the NSAE returns to normal, or until the investigator believes that further follow-up is not necessary. 9.2 Recording and assessment of adverse events

Attention should be paid to the collection of AE during the whole research process. The following are the variables that should be recorded for each AE: onset and stop time, severity, measurements, causal relationship with intervention, outcomes and whether it is a serious adverse event.

The severity of adverse events is assessed as follows: Mild: usually temporary, and not affecting daily activities; Moderate: causing discomfort and affecting normal activities, thought tolerable and not requiring participants to take any medication. Severe: disrupting daily activities and intolerable, requiring participants to take medication immediately. With regard to the causal-effect relationship, medical adverse events are divided into five categories: definite, probable, possible, unlikely, and unrelated. Only "definite" and "probable" are counted as adverse events. The severity assessment of adverse events is as follows:

- 1) Mild: usually temporary and does not affect daily activities.
- Moderate: discomfort, affect normal activity and does not require medication to alleviate symptoms.
- 3) Serious: not endurable, affect daily activities and require medication immediately.

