Calorie restriction (CR) is an effective method to reduce weight and severity of obesity related diseases, but traditionally it requires constant effort to cut down calorie intake every day (continuous calorie restriction, CCR) and may lead to potential adverse effects on the body. Intermittent calorie restriction (ICR) refers to maintaining no or very-low calorie intake periodically, which means alternating normal diet and fasting for a certain period to prevent and treat various diseases. The most common ICR schemes include time restrict fasting (TRF) or time restrict eating (TRE), alternate day fasting (ADF) and fasting for two days per week (5:2 diet). ICR can effectively reduce weight, lower blood pressure, improve lipid profile and reduce oxidative stress. It also facilitates glucose control by increasing insulin sensitivity and improving  $\beta$  Cell function. Recent studies have proved the effectiveness of TRE and ADF on reducing weight and improving cardiometabolic risk factors. However, effect of ICR, especially 5:2 diet, on MASLD patients has been rarely studied. A few studies have found ICR could reduce liver enzymes in MASLD patients, but they were less accurate because fat content of the whole liver, as well as of different liver segments were not quantitatively evaluated before and after treatment. More importantly, no study directly compared the therapeutic effect of ICR and CCR on MASLD currently.

2. Aim of the study

In the present study, we carried out a randomized, controlled, open-label clinical trial to investigate the efficacy and safety of ICR in MASLD patients with abnormal glucose metabolism. For ICR group, we adopt the 5:2 scheme which was related to stronger patient compliance. The control group received traditional CCR. Two groups were instructed to keep overall calorie restriction to similar degree during 12 weeks of treatment. The changes of LFC of the whole liver, as well as of different liver segments measured by MRI-Proton Density Fat Fraction (MRI-PDFF) were compared between two groups. We hypothesize that ICR will be more effective than CCR in reducing LFC and other metabolic risk factors.

- 3. Research design
- 3.1 Overall design

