5.1 Dietetic intervention

- ICR group: Participants in ICR group were instructed to ensure 2 successive days of fasting-mimicking and 5 days of recovery per week. On fasting-mimicking days, the participants were instructed to consume approximately 500 kcal/day and they were provided with plant-based meal replacement (ZhenBaiNian nutrition bar, Beijing Winlife Research Institute of Nutrition, Health, Food Science, and Technology, China) to improve adherence and ensured adequate intake of micronutrients. In the rest 5 days of recovery per week, participants were allowed to consume their usual diet. Main ingredients of this meal replacement are as follows:
  - Main ingredients: isomaltooligosaccharide solution, high-protein and high-fiber crispy grain (soy protein isolate, rice, polydextrose, calcium carbonate), Chia seed, resistant dextrin, coconut potato, salty vegetable grain, etc.

Table 1. Information of nutrition bar used in this trial			
	Per 100g	%NRV	

energy	355.4 kcal	18%
protein	15.4 g	26%
Fat	12.4 g	21%
Trans fats (acids)	0 g	
Polyunsaturated fatty acids	3.6 g	
carbohydrate	34.0 g	11%
dietary fiber	23.5 g	94%
sodium	261 mg	13%
vitamin A	565 µg	71%
vitamin D	2.5 µg	50%
vitamin E	8.05 mg	58%
Vitamin B1	1.30 mg	93%
Vitamin B2	1.30 mg	93%
Vitamin B6	1.30 mg	93%
Vitamin B12	0.80 µg	33%
vitamin C	67.7 mg	68%
nicotinic acid	13.50 mg	96%
folic acid	328 µg	82%
Pantothenic acid	3.17 mg	63%
Biotin	3.8 µg	13%
phosphorus	257 mg	37%
potassium	318 mg	16%
magnesium	72 mg	24%
calcium	433 mg	54%
iron	6.7 mg	45%
zinc	5.25 mg	35%
selenium	10.0 µg	20%
copper	0.44 mg	29%
fluorine	0.06 mg	6%
manganese	1.00 mg	33%
ω~ 6 Linoleic acid	1.6 g	
ω~ three α- linolenic acid	2.0 g	

Manufacturer: Beijing Wanlaikang Nutrition and Health Food Science and Technology Research Institute Co., Ltd

Product standard No.: Q/CPKWC 0085

> Food production license No.: SC10611141312769

 CCR group: Participants in CCR group were instructed to consume the prescribed calories (25 kcal / kg × [height (cm) – 100] kg) every day by eating conventional food without time restriction.

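### Section 9.1 defines a non-serious adverse event by the word *unforeseeable*, which, read literally, leaves out new but predictable symptoms of calorie restriction and can under-record harms in both arms

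*Combined protocol and SAP*

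**What the plan says.** Section 2 states the aim as "to investigate the efficacy and safety of ICR in MASLD patients with abnormal glucose metabolism", so safety is part of it. In section 5.1 the ICR arm has two successive low-intake days a week: "On fasting-mimicking days, the participants were instructed to consume approximately 500 kcal/day". The CCR arm has a daily target of 25 kcal for each kg of (height in cm minus 100).

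The definition of a non-serious event (NSAE) in section 9.1 has two limbs. The first is "Non-Serious Adverse Event (NSAE) refers to an unforeseeable medical condition that occurs during or after the treatment". The second is "or an event that makes the original condition worse". The paragraph then adds "The occurrence of NSAE does not necessarily have a causal relationship with the intervention" and "Adverse medical conditions include symptoms (such as nausea and chest pain), physical signs (such as tachycardia and hepatomegaly) or abnormal examination results".

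Section 9.2 says "Attention should be paid to the collection of AE during the whole research process". After naming five causality categories it says "Only 'definite' and 'probable' are counted as adverse events". Section 9.3 requires reporting regardless of relatedness, but only for serious events. Table 2 marks adverse events at V1 to V9 with no distinction by arm. Section 6 lists no safety outcome. Section 11.2 names chi-square or Fisher's exact tests for categorical variables in general and specifies no adverse event comparison.

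**The concern.** The usual test for an adverse event is that it is untoward, not that it could not have been foreseen. Symptoms such as hunger, dizziness or fatigue during marked calorie restriction are predictable; these are my examples, since the protocol lists no expected harms. In a participant who did not have such a symptom before, it is neither unforeseeable nor a worsening of the original condition. A recorder who takes section 9.1 at its word would leave it off the form.

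Because section 6 has no safety outcome, the adverse event records are the main evidence on how well either diet was tolerated. If predictable symptoms are missing from them, tolerability is overstated in both arms, and a comparison between arms rests on whatever was left after filtering.

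**Working it through.** The plan gives no adverse event rate, safety margin or safety power, so there is no figure to reproduce. The check is of the text, followed by an illustration with assumed rates.

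**Text: does any passage restore a new, expected, non-serious symptom?**

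1. *Second limb of 9.1.* It carries no foreseeability test, but covers only worsening of the original condition. A new symptom has to qualify under the first limb.
2. *The sentence naming nausea.* It says what form an adverse condition can take: symptom, sign or abnormal result. It neither repeats nor removes *unforeseeable*. It pulls against the literal reading without overruling it.
3. *The causality sentence in 9.1.* It removes a relatedness test. Expectedness is a different attribute.
4. *Collection rule in 9.2 and Table 2.* These say when to collect events, and depend on 9.1 for what an event is. Neither tells staff to omit expected events, and neither tells them to include them.
5. *Counting rule in 9.2.* It sorts by causality. It does not mention expectedness and can act only on events already recorded.
6. *Section 9.3.* The clause that disregards relatedness concerns serious events only.

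So the literal exclusion is not reversed anywhere, although the paragraph is ambiguous against its own examples.

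**Illustration: effect on the difference between arms.** Let *u* be the risk of an unforeseeable event (same in both arms), *e* the risk of an expected symptom in an arm, and *f* the share of expected events dropped. With the two kinds of event independent:

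recorded any-event risk = 1 − (1 − u)(1 − e(1 − f))

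ICR minus CCR = (1 − u)(1 − f)(e_ICR − e_CCR)

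All values below are assumptions, with u = 5%. For 30% v 10% and nothing dropped, ICR is 1 − 0.95 × 0.70 = 33.5% and CCR is 1 − 0.95 × 0.90 = 14.5%, a difference of 19.0 points. With half dropped it is 0.95 × 0.5 × 20 = 9.5 points.

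| Expected symptoms, ICR v CCR | None dropped | Half dropped | All dropped |
|---|---|---|---|
| 30% v 10% | 19.0 | 9.5 | 0 |
| 20% v 10% | 9.5 | 4.7 | 0 |
| 10% v 10% | 0 | 0 | 0 |
| 10% v 20% | −9.5 | −4.7 | 0 |

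The recorded difference shrinks by the factor (1 − f) whichever arm has more expected symptoms. In the last row the harm concealed is in CCR. With equal risks the difference is unbiased, but each arm is still under-counted: 14.5% falls to 5% if all expected events are dropped. The table assumes the same *f* in both arms. The trial is open-label, so the shares could differ, and the difference could then move either way.

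**The case against.** The strongest reply is that *unforeseeable* is probably a slip for *untoward* and that nobody would apply it literally. Section 9.1 itself gives nausea as an example. Predictable diet effects are plausibly the events most likely to be rated definite or probable, so on the literal reading 9.1 would discard much of what 9.2 says to count. No passage instructs staff to omit anything. All of this stands as evidence that the text is ambiguous and that the literal meaning may not be intended. It does not settle how the word was applied: this is the only NSAE definition, and the ambiguity leaves each recorder to decide.

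A reader might go further and infer that the expected harms of the 500-kcal days are excluded, and hence that the safety comparison is biased towards no harm from ICR. There is something behind this: very low intake is prescribed only in ICR, whereas the CCR formula gives 25 × 55 = 1,375 to 25 × 80 = 2,000 kcal a day for assumed heights of 155 to 180 cm. But the documents do not support the inference. They contain no adverse event rates, no list of expected ICR harms and no evidence that events were omitted. The one diet harm that they anticipate, in section 1, is attributed to daily continuous restriction, which is the control arm. The definition is the same for both arms, and no comparative safety analysis is specified that could be called biased.

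**Conclusion.** The definition is wrong as written and should be changed. Read literally, it leaves out new but predictable non-serious symptoms, nothing elsewhere restores them, and following it would under-record diet-related harms in both arms of a trial that states a safety aim.

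The effect on the ICR–CCR difference is conditional. If expected symptoms are more frequent in ICR, and a similar share is dropped in each arm, the recorded difference shrinks in proportion to that share: by half if half are dropped, and to nothing if all are. If they are equally frequent, equal dropping leaves the difference unbiased. If they are more frequent in CCR, it is CCR harm that is hidden. The rates are assumed throughout, so neither size nor direction can be derived from the documents.

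The causality filter in section 9.2 is a separate restriction and conflicts with 9.1's statement that causality is not required. Correcting one would leave the other in place.

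**What to change.** In section 9.1, replace the phrase built on *unforeseeable* with: *any untoward medical occurrence, whether or not expected and whether or not related to the intervention*. Keep the limb on worsening. Apply the definition identically in both arms at the contacts already scheduled in Table 2, and tabulate participants with at least one event by arm. Section 7 mentions adverse events only at weeks 2, 4, 8 and 12, so it should be aligned with Table 2. A fixed checklist of diet-related symptoms, asked the same way in both arms, is an optional addition.

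Section 3.1 describes the trial as conducted between July 2020 and July 2021. If data collection is complete, the report should state how *unforeseeable* was applied, and the existing case report forms should be re-reviewed before any comparative safety conclusion is drawn. Re-review can recover only what was written down.

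The cost is one line of text and one table or, after the fact, a pass through the forms of 60 participants. The downside is that more mild events will be recorded.

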This 12-week, open-label, randomized, controlled, parallel-group trial was conducted at Zhongshan Hospital Fudan University between July 2020 and July 2021 (ClinicalTrials.gov, NCT04283942). The trial was initiated by the researcher, performed in accordance with the ethical principles of the Declaration of Helsinki and approved by the Ethics Committee of Zhongshan Hospital Fudan University (approval number: B2019-256). A total of 60 patients were enrolled in the trial, and written informed consent was obtained from all patients. 3.2 Randomization and masking

The simple randomization method was used to ensure similar baseline characteristics between two groups. The randomization scheme will be provided by the Statistics Department of School of Public Health of Fudan University (generated by SAS software), and randomization will be completed by staff unrelated to this trial. According to the randomization scheme, a random envelope marked with the treatment number will be made and assigned for each subject according to the order of enrollment. The treatment will be carried out according to the arrangement of corresponding scheme.

- 4. Study participants
- 4.1 Inclusion Criteria
- Age 18-70
- Diagnosed as fatty liver by ultrasound or magnetic resonance imaging
- BMI ≥ 24 kg/m^2
- Abnormal glucose metabolism: (meeting at least one):
  - Impaired glucose regulation: fasting blood glucose ≥ 100 mg/dL, postprandial blood glucose ≥ 140 mg/dL or HbA1c ≥ 5.7%
  - 2) Diabetes mellitus: diabetic symptoms + plasma glucose concentration ≥ 200 mg/dL at any time or fasting plasma glucose concentration ≥ 100 mg/dL or OGTT 2 h plasma glucose concentration ≥ 200 mg/dL

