6.3 Other pre-specified outcomes

- Change of fat mass and lean mass measured by a bioimpedance analyzer
- Change of abdominal adiposity measured by MRI: visceral adipose tissue and subcutaneous adipose tissue
- Change of liver stiffness measured by liver transient elastography
- Change of insulin sensitivity: fasting insulin and HOMA-IR (fasting glucose in mmol/L x fasting insulin in  $\mu$ U/mL)/22.5)
- 7. Follow-up visits
- (1) Screening visit (V0): The purpose of this visit is to confirm subjects' eligibility and interest in the proposed study, and obtain informed consent, relevant medical history (including diabetes, fatty liver, alcohol drinking history, hepatitis history, drug use, etc.), physical measurements (weight, height, waist circumference and blood pressure), and laboratory measurements (OGTT, HbA1c, liver and renal functions, electrolytes, hepatitis markers, etc). H-Proton Magnetic Resonance Spectroscopy (H-MRS), MRI-Proton Density Fat Fraction (MRI-PDFF) and liver transient elastography were applied to evaluate the fatty liver. Body composition analysis and other examinations were performed. Relevant laboratory and imaging examination results within 2 weeks before screening can be approved.
- (2) Baseline visit (V1): The baseline follow-up was scheduled within 2 weeks after the screening period. Physical examination was conducted. Subjects will be required to record their diet and steps for 3 days before day 0 and the average of calorie consumption and steps will be used as baseline reference. Randomization will be conducted.
- (3) Follow up and termination visits (V2 V9): At each visit, diet and step records will be collected. At week 2, 4, 8 12, physical measurements, fasting glucose and adverse events will be recorded. Nutritionists will provide dietary advice and help subjects to keep calorie

restriction and a balance of nutrients. On this basis, liver and renal functions, electrolytes, fasting blood glucose and lipids profiles will be measured at week 4. At week 12 (termination visit), OGTT, H-MRS, MRI-PDFF, liver transient elastography and body composition analysis will be added. At week 1, 3, 6, 10, only telephone follow-up will be conducted.

(4) Post-intervention visit (V10): At 4 weeks after the intervention (week 16), body weight will be investigated by telephone.

	Screening	Baseline								Termin ation	Post- interve ntion
Visit	V0	V1	V2	V3	V4	V5	V6	V7	V8	V9	V10

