#### 9.3 Treatment of AE

The patients with mild AE can continue the intervention and visits. Those with SAE should stop intervention and take corresponding treatment in time.

Once NSAE happens, the severity, duration, treatment and outcome of adverse reactions should be explained. If other drugs are used at the same time during the trial, it shall be recorded in a timely manner on case report forms.

All SAEs, whether related to the intervention or not, should be reported and recorded in the adverse event report form of the case report form, recording the occurrence time, severity, duration, measures taken, etc. Researchers have the responsibility to notify the Ethics Committee within 24 hours.

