#### 10. Data management

All case report forms for each participant should be filled out by study staff in a timely manner. The case report form should be double-checked for potential errors or missing data. All data, including questionnaires, physical examinations, laboratory and other examinations, will be filled in the subject's chart. Original documents, participants' charts, and CRF forms will be stored in the study office. All data will be double-entered by researcher staff.

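### Section 9.2 counts only events rated definite or probable as adverse events, although section 9.1 defines a non-serious adverse event without requiring causality

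*Combined protocol and SAP*

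**What the plan says.** Section 9.1 defines the non-serious adverse event (NSAE) without a causality condition: "The occurrence of NSAE does not necessarily have a causal relationship with the intervention". Section 9.2 makes causality one item among several to be captured: "The following are the variables that should be recorded for each AE: onset and stop time, severity, measurements, causal relationship with intervention, outcomes". It then sets the rating scale, under which "medical adverse events are divided into five categories: definite, probable, possible, unlikely, and unrelated", and follows it with the counting rule: "Only 'definite' and 'probable' are counted as adverse events".

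Two other places deal with NSAEs or with adverse events in general. Section 7 says that at the clinic visits "physical measurements, fasting glucose and adverse events will be recorded", and section 9.3 says "Once NSAE happens, the severity, duration, treatment and outcome of adverse reactions should be explained". Neither sets a causality limit, and neither says how events are to be counted.

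For serious adverse events (SAEs), section 9.3 requires reporting and recording whether or not the event is related. Section 11.2 has no adverse event analysis, only a general sentence naming chi-square or Fisher's exact tests for categorical variables.

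**The concern.** The definition and the counting rule cannot both be followed. A headache rated possible, or a cold rated unrelated, is an adverse event under section 9.1 and is not counted as one under section 9.2. The rule removes even the possible category.

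This matters because section 2 names safety of intermittent calorie restriction (ICR) as an aim alongside efficacy. A reader of an adverse event table would expect the section 9.1 meaning, but a table that follows section 9.2 shows only events that someone attributed to the diet. Section 3.1 describes the study as open-label. No blinded causality assessment is described, and the documents do not say who rates causality, so the filter may be applied by someone who knows the arm.

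Unequal attribution is not in itself bias. If one diet causes more events, accurate rating will give that arm a larger definite/probable share. The difficulty is that the filtered count alone cannot tell this apart from a rater who attributes more readily in one arm. An all-cause count beside it helps.

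**Working it through.** **Comparison of the text.** The plan has no figure to reproduce. The non-serious events are handled as follows.

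| Causality rating | NSAE under 9.1? | Counted under 9.2? |
|---|---|---|
| Definite | Yes | Yes |
| Probable | Yes | Yes |
| Possible | Yes | No |
| Unlikely | Yes | No |
| Unrelated | Yes | No |

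Three of the five categories leave the count. I looked for a passage that puts them back. Sections 7 and 9.3 concern recording and explaining; the all-causality rule in section 9.3 covers SAEs only; section 11.2 is generic; sections 6.1 to 6.3 list no adverse event outcome. Section 9.2 holds the only counting rule. The conflict is about counting: nothing tells staff to discard lower-rated events.

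**Illustration of size.** The documents give no adverse event rate and no attribution share, so every event rate and share below is an assumption. From the plan I take 30 per arm (section 11.1), the two-sided 0.05 level and Fisher's test (section 11.2, which does not name it for adverse events). I assume at most one event per affected participant.

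Counted rate = true rate × share rated definite or probable. The probability of P<0.05 is the exact sum over all pairs of binomial counts (a, b), each from 0 to 30, of Pr(a) × Pr(b) × [Fisher P<0.05].

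*No true difference (40% in both arms); any attribution gap is due to rater bias only:*

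| Attribution, arm 1 v arm 2 | Counted rates | P<0.05, 30 per arm | P<0.05, 25 per arm |
|---|---|---|---|
| All events counted | 40% v 40% | 2.6% | 3.0% |
| 40% v 40% | 16% v 16% | 1.8% | 2.0% |
| 45% v 35% | 0.40×0.45 = 18% v 0.40×0.35 = 14% | 2.9% | 2.9% |
| 50% v 30% | 20% v 12% | 6.5% | 6.0% |
| 60% v 20% | 24% v 8% | 25.5% | 21.8% |

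The 25-per-arm column allows for roughly the 15% dropout in section 11.1 (30 × 0.85 = 25.5).

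*True difference of 60% v 20%*, taken as 20% background in both arms plus 40% caused by the diet in one arm, with 10% of background events rated definite or probable. Counted rate in the affected arm = 0.20×0.10 + 0.40×c, against 0.20×0.10 = 2% in the other, where c is the share of caused events rated definite or probable.

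| Count used | Counted rates | Power, 30 per arm | Power, 25 per arm |
|---|---|---|---|
| All events | 60% v 20% | 85.1% | 78.8% |
| c = 0.60 | 0.02 + 0.24 = 26% v 2% | 67.2% | 56.4% |
| c = 0.80 | 0.02 + 0.32 = 34% v 2% | 89.6% | 82.9% |

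At 30 per arm, c = 0.74 gives 84.7% and c = 0.75 gives 85.6%, so the filter breaks even near c = 0.75. It can raise or lower power, depending on how accurate the rating is.

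**The case against.** The strongest reply is that this is one sentence of loose wording in a document that is loose elsewhere. Section 9.3 slides from NSAE to adverse reactions within a sentence, and section 9.2 gives the severity scale twice with different labels. The sentence may have been meant to define a related subset, which is a legitimate thing to report. A five-level scale that includes unrelated also presupposes that unrelated events are captured. No adverse event outcome or table is specified, so no planned count is shown to be wrong. The illustration rests wholly on assumed inputs, and filtering with equal attribution creates no excess of false positives (1.8% against 2.6%). An all-cause count is not free of open-label bias either, since participants who know their arm may report differently.

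Most of this stands as a limit on the consequences. Neither the direction nor the size of any bias is shown, modest attribution gaps hardly matter, and the lower-rated events are probably recoverable. That last point is not certain, because section 9.3 expressly ties only SAEs to the adverse event form.

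It does not remove the conflict. The sentence says what is counted as an adverse event, not what is counted as related. If a related subset was meant, the text still needs the same correction, and an all-cause count is still missing beside it. That no adverse event analysis is specified elsewhere leaves this sentence as the only rule an analyst could follow.

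**Conclusion.** The concern holds: section 9.2 is wrong as written. Followed literally, it leaves non-serious events rated possible, unlikely or unrelated out of the adverse event count, against the definition in section 9.1.

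Confidence in the textual conflict is high. The effect on results is unknown, because the documents give no event rates or attribution shares; under the assumptions above, only a large biased gap in attribution distorts a between-arm test, and power can move either way.

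SAE reporting, the scheduled laboratory tests, the termination criteria in section 4.3 and the primary outcome are untouched. This should be fixed, but it does not threaten the main conclusion of the trial.

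**What to change.** The trial is described as already carried out ("This 12-week, open-label, randomized, controlled, parallel-group trial was conducted at" a single hospital, with dates given), so the data come first and the wording second.

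1. Check the case report forms. Section 10 says "CRF forms will be stored in the study office", so this should be possible. Establish whether events rated below probable were entered.
2. If they were, report all adverse events by arm regardless of causality, with the definite/probable events as a separate, labelled subset.
3. If they were not, say so, and label the reported rates as attributed events only.
4. In either case, state who rated causality and whether they knew the arm.
5. Reconcile sections 9.1 and 9.2 so that all adverse events are counted and related events form a subset with a stated cut-off. Record this as a dated change, so that the rule actually used remains visible.
6. In the same edit, resolve a separate wording mismatch: the SAE definition in section 9.1 refers to events caused by the intervention, while section 9.3 covers SAEs whether related or not.

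The cost is one check of the forms, one extra table and one recorded wording change. Reported rates may rise if lower-rated events occurred and were kept. If they were never entered, the all-cause table cannot be produced and disclosure is the only remedy.
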